### **Statistical Methodology Specification**

Endpoint / Variables

• The COPD prescription for maintenance therapy at each visit

Model Specification

• Chi-square test or Fisher's exact test

• Bonferroni-corrected P value will be calculated when the P value of Chi-square test or Fisher's exact test is less than 0.05.

Model Checking & Diagnostics

• N/A

Model Results Presentation

• The number and percentage of patients who receive any maintenance treatment prescription will be reported.

• The number and percentage of patients who receive different pattern of the maintenance treatment prescription will be reported separately.

• The P value will be reported.

Subgroup Analyses
• N/A
Sensitivity Analyses
• N/A
Supportive Analyses
• N/A

## 6.6.2. Sensitivity Analysis

None.

## 6.7. Secondary Analysis

### 6.7.1. Secondary Endpoints

- The COPD prescription for each maintenance therapy at baseline.
- The disease burden of the patients, including mMRC score, CAT score at baseline, number of exacerbations in previous 1 year
- The change of COPD prescription for maintenance therapy.
- Each COPD treatment used at 3 months.

### 6.7.2. Summary Measure

- **The COPD prescription for each maintenance therapy at baseline:**
  - Descriptive analysis of categorized covariates (see 6.1.5 Covariates and Other Strata) will be summarized.
  - Adjusted odds ratios (ORs) and 95% confidence intervals (95% CIs) of each covariates based on univariate logistic regression (see 6.7.4. Model Specification).
  - The number and percentage of patients in each pattern of maintenance treatment will be summarized by the covariates used in the multivariate logistic regression.
  - Separate analyses will be performed for stable and exacerbating patients
- **The disease burden of the patients**
  - Number and percentage in different mMRC score intervals, CAT score intervals, Baseline GOLD 2019 group, Gold grade, numbers of historic exacerbation according to the usage of different historic treatments.
    - mMRC score intervals are defined as : Grade0, Grade1, Grade2, Grade3, Grade4
    - CAT categories are defined as: ≤10, 11-20, 21-30, 31-40.
    - Baseline GOLD 2019 group is defined as: A, B, C, D.
    - Gold grade is defined as: I, II, III, IV.
  - Mean and standard deviation of mMRC score, CAT score, number of historic exacerbations according to the usage of different historic treatments.
  - The above analyses will also be performed for Tier 2 and 3 hospitals separately.
- **The change of COPD prescription for maintenance**

The number and percentage of participants in each category across the different study time points.

The categories are defined as:

Categories	Definition
Stepped up	Adding another maintenance treatment: The latter visit increased by any one or more of LAMA, LABA, or ICS treatments compared to the previous visit.
Stepped down	Withdraw any of the maintenance medication but kept the maintenance treatment: The latter visit reduced by any one or more of LAMA, LABA, or ICS treatments compared to the previous visit.
Stopped	Stopped all LAMA, LABA and ICS treatments.
Switched	Between LAMA and LABA; Between LAMA/LABA and ICS/LABA.
Remained	The LAMA, LABA and ICS combinations in the prescription in the latter visit are the same as the combinations in the previous visit; No LAMA, LABA and ICS in the prescription in the latter visit and previous visit.

The time points are coupled as:

Population	Time points	Summary Measure
Stable patients	3 months vs baseline	
-Descriptive analysis of categorized covariates (see 6.1.5 Covariates and Other Strata) will be summarized.
 
-Adjusted odds ratios (ORs) and 95% confidence intervals (95% CIs) of each covariates based on univariate multinomial logistic regression (see 6.7.4. Model Specification).
 
-The number and percentage of patients in the change of COPD prescription for maintenance therapy will be summarized by the covariates used in the multivariate multinomial logistic regression.

Exacerbation patients	3 months vs pre baseline	Descriptive analysis of the change of COPD prescription for maintenance therapy.
	1-week/ discharge follow-up vs pre baseline	
-Descriptive analysis of categorized covariates (see 6.1.5 Covariates and Other Strata) will be summarized.
 
-Adjusted odds ratios (ORs) and 95% confidence intervals (95% CIs) of each covariates based on univariate logistic regression (see 6.7.4. Model Specification).

	3 months vs 1-week/ discharge follow-up	
-The number and percentage of patients in the change of COPD prescription for maintenance therapy will be summarized by the covariates used in the multivariate logistic regression.

The above analyses will also be performed for Tier 2 and 3 hospitals separately.

In addition, the following content will also be summarized:

(1) The change of treatment in individual treatments by each maintenance treatment

The number and percentage of patients who stopped or started a maintenance treatment prescription at the time points (including 1-week follow-up/discharge follow-up compare to baseline, 3 months follow up compare to baseline, 3 months follow up compare to 1-week follow-up/discharge follow-up) will be calculated.

The above analyses will also be performed for Tier 2 and 3 hospitals separately.

## (2) LAMA, LAMA/LABA, ICS/LABA step up situation

The number and percentage of patients who stepped up or not stepped up to any treatment at the time points (including 1-week follow-up/discharge follow-up compare to pre baseline, 3 months follow up compare to baseline (stable patients) or pre baseline (exacerbating patients), 3 months follow up compare to 1-week follow-up/discharge follow-up) will be calculated.

The definition of step up to any treatment for patients with LAMA: LAMA at baseline switched to MITT, SITT, LAMA/LABA or ICS/LABA.

The definition of step up to any treatment for patients with LAMA/LABA: LAMA/LABA at baseline switched to MITT or SITT.

The definition of step up to any treatment for patients with ICS/LABA: ICS/LABA at baseline switched to MITT or SITT.

Comparison will be considered in two directions. For each specific treatment (LAMA, LAMA/LABA, ICS/LABA), the overall significant test will be conducted to detect the difference of stepping up to MITT and SITT (and LAMA/LABA, ICS/LABA when the treatment at baseline is LAMA; Chi-square test or Fisher's exact test will be used and Bonferroni-corrected P value will be calculated when the P value of Chi-square test or Fisher's exact test is less than 0.05). Additionally, when the stepping up situations is MITT, significant test will be conducted to detect the difference of different baseline treatments. Chi-square test or Fisher's exact test will be used and Bonferroni-corrected P value will be calculated when the P value of Chi-square test or Fisher's exact test is less than 0.05; similarly, for SITT. Chi-square test or Fisher's exact test will be used.

## (3) MITT, SITT step down situation

The number and percentage of patients who stepped down or not stepped down to any treatment, stopped all treatment or not stopped all treatment at the time points (including 1-week follow-up/discharge follow-up compare to pre baseline, 3 months follow up compare to baseline (stable patients) or pre baseline (exacerbating patients), 3 months follow up compare to 1-week follow-up/discharge follow-up) will be calculated.

The definition of step up to any treatment for patients with MITT: MITT at baseline/pre baseline/1-week follow-up/discharge follow-up switched to LAMA, LABA, LAMA/LABA or ICS/LABA.

The definition of step up to any treatment for patients with SITT: SITT at baseline/pre baseline/1-week follow-up/discharge follow-up switched to LAMA, LABA, LAMA/LABA or ICS/LABA.

Comparison will be considered in two directions. For each specific treatment (MITT and SITT), the difference of stepping down to LAMA, LABA, LAMA/LABA and ICS/LABA will be compared. Chi-square test or Fisher's exact test will be used and Bonferroni-corrected P value will be calculated when the P value of Chi-square test or Fisher's exact test is less than 0.05.

Additionally, when the stepping down situations is LAMA, significant test will be conducted to detect the difference of different baseline treatments; similarly, for LABA, LAMA/LABA, ICS/LABA. Chi-square test or Fisher's exact test will be used.

#### (4) COPD prescription for maintenance therapy step up situation of different patients

The number and percentage of patients who stepped up or not stepped up to any treatment, stepped down or not stepped down to any treatment at the time points (including 1-week follow-up/discharge follow-up compare to pre baseline, 3 months follow up compare to baseline (stable patients) or pre baseline (exacerbating patients), 3 months follow up compare to 1-week follow-up/discharge follow-up) will be calculated and compared by the following covariates: Age (below 65 years old, 65 years old and above), Gender (female, male), Smoking status (Used to smoke, Current smoking, Never smoking), Cardiovascular Disease (yes, no), Concurrent asthma with COPD (yes, no), Past history of tuberculosis (yes, no), Annual income (KRMB) (<30, 30-80, >80), Gold grade (I, II, III, IV), Baseline CAT score ( $\leq$ 10, 11-20, 21-30, 31-40), Type of hospital (Tier 2, Tier 3), History of exacerbation (None, Moderate, Previous hospitalized).

Chi-square test or Fisher's exact test will be used and Bonferroni-corrected P value will be calculated when the P value of Chi-square test or Fisher's exact test is less than 0.05.

#### (5) Change of CAT score when treatment stepping up and stepping down

CAT score will be described by visits (baseline and 3 months follow up) and calculated the change from baseline. These analyses will be summarized by the treatment stepping up and stepping down situation.

- **Each COPD treatment used at 3 months**
  - Number and percentage of patients who actually use each maintenance treatment at 3 months will be summarized
  - The above analyses will also be performed for Tier 2 and 3 hospitals separately.

#### 6.7.3. Population of Interest

The secondary analyses will be based on the enrolled population.

#### 6.7.4. Statistical Analyses / Methods

One of the secondary objectives of this study is to examine factors (include baseline disease severity and baseline socio-economic factors) that are associated with different patterns of maintenance treatment at baseline. Separate analyses will be performed for stable and exacerbating patients, since it is possible that the factors that influence a physician's choice of treatment may differ between the two conditions. Multivariate logistic regression will be used to identify influence factor for having a certain maintenance treatment versus none.

Separate analyses of disease burden will be performed for stable and exacerbating patients.

#### Statistical Methodology Specification

Endpoint / Variables
• COPD prescription for each maintenance therapy at baseline
Model Specification

Univariate / Multivariate logistic regression with binary endpoint.

- Dependent variable: each pattern of the following maintenance treatment at baseline. The categories will be binary, e.g. treatment class used: Yes/No.
  - Long-Acting Muscarinic Antagonist [LAMA]
  - Long-Acting Beta-Agonist [LABA]
  - Dual bronchodilator
  - Inhaled corticosteroid [ICS]/ Long-Acting Beta-Agonist [LABA]
  - Triple therapy
  - Theophylline
  - N-acetyl cysteine/carbocysteine
  - MITT
  - MITT or SITT
- Independent variables: variables defined in 6.1.5 Covariates

### Model Checking & Diagnostics

- Collinearity diagnostics
- The covariates with P-value less than 0.1 in univariate logistic regression and fixed variables (including Age, Gold grade, Baseline CAT score, Type of hospital and History of exacerbation) will be included in the multivariate logistic regression model.

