### **3.2.2 Sampling**

For this study, around 1500 patients with COPD will be enrolled including stable patients and patients with exacerbations. It is planned that approximately equal number of patients will be recruited from Tier 2 and Tier 3 hospitals. After 500 patients have been recruited a review will be carried out to assess whether an adequate number of patients from each of the 3 cohorts defined in section 3.1 has been enrolled. At this point, recruitment policy might be changed to ensure an adequate distribution across type of hospital and type of patient. Thereafter, recruitment to each cohort will be monitored weekly and further corrective action will be taken if needed.

At least one site in each of the main provinces of China will be selected. There is a variability of spirometry and inhaled therapy availability across Tier 2 hospitals, although this is improving. As the Government is actively encouraging patients to shift from Tier 3 to Tier 2 hospitals, the study will only include Tier 2 hospitals that, at a minimum have respiratory department, supply of LAMA and ICS/LABA, and facilities for spirometry, since this will be the minimum standard of care for patients with COPD in Tier 2 hospitals in the future.

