### **3.3.2.5 Physician survey**

Physician will be asked questions on why they follow their prescription practices. The survey will give brief idea on grounds which physicians prescribe treatment to patients.

- In addition to the severity of the patient's disease, which factors have influenced your prescription for THIS patient? (choose one or more options)
  - A. Patient or family 's economic condition
  - B. Patient's reimbursement position
  - C. Drug availability of your hospital
  - D. Patient's ability to use the inhaler
  - E. Patient's preference
  
- If none of the above factors applies, which treatment would you choose for THIS patient? (Choose one option)
  - A. None
  - B. SABA or SAMA (or both)
  - C. LAMA or LABA
  - D. LAMA+LABA
  - E. ICS+LABA
  - F. ICS+LABA+LAMA

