### 6.1.4. Multicenter Studies

It is estimated that 750 patients each from tier 2 and tier 3 hospitals will be enrolled to provide

adequate representation on healthcare status for COPD in China. All analyses of primary, secondary [REDACTED] will be performed for Tier 2 and 3 hospitals separately.

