### Model Results Presentation

- Adjusted odds ratios (ORs) with 95% confidence intervals (95% CIs) and P-value for each covariates.

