### Model Checking & Diagnostics

- Collinearity diagnostics
- The covariates with P-value less than 0.1 in univariate (multinomial) logistic regression and fixed variables (including Age, Gold grade, Baseline CAT score, Type of hospital and History of exacerbation) will be included in the multivariate (multinomial) logistic regression model.

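### In pooled-tier runs, the hospital-tier odds ratios and tests ignore site; with any positive within-tier site correlation their intervals are too narrow

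*SAP*

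**What the plan says.** SAP 6.7.4 specifies ordinary binary logistic regression for each treatment pattern at baseline. For change of prescription it specifies multinomial regression (stable patients) or binary regression (exacerbating patients). In both model tables hospital tier is a fixed variable: "Type of hospital and History of exacerbation) will be included in the multivariate logistic regression model" and, for change of prescription, "will be included in the multivariate (multinomial) logistic regression model". SAP 6.1.2 repeats the rule. Other covariates enter if their univariate P-value is below 0.1. The output in both tables is "Adjusted odds ratios (ORs) with 95% confidence intervals (95% CIs) and P-value for each covariates".

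SAP 6.7.2(4) compares step-up and step-down between levels of 11 factors by chi-square or Fisher's exact test. Two of them are "Type of hospital (Tier 2, Tier 3), History of exacerbation (None, Moderate, Previous hospitalized".

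Site is not in the covariate list of SAP 6.1.5. No site effect, GEE or cluster-robust variance appears in the visible text; redacted parts cannot be checked. The multicentre section, SAP 6.1.4, provides only that the analyses "will be performed for Tier 2 and 3 hospitals separately". In SAP 6.7.2 the change-of-prescription analyses carry a different sentence: "The above analyses will also be performed for Tier 2 and 3 hospitals separately". Protocol 3.1 plans around 35 sites, plus or minus 5.

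**The concern.** All patients of a hospital share its tier, so a tier contrast is a contrast between groups of hospitals. Ordinary logistic regression and chi-square tests treat patients as independent. If hospitals of the same tier differ in prescribing beyond chance, the tier standard errors are too small.

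The documents make some within-tier correlation plausible. Protocol 3.2.2 states: "There is a variability of spirometry and inhaled therapy availability across Tier 2 hospitals". The physician survey in Protocol 3.3.2.5 offers "Drug availability of your hospital" as an influence on the prescription. The study is about prescribing in Tier 2 and Tier 3 hospitals, so a tier odds ratio with a small P-value will attract attention. Differences between a few hospitals could then be read as a tier effect.

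The SAP also leaves open which run carries the tier term. A run within one tier cannot estimate it, yet SAP 6.1.4 says the analyses are run by tier.

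**Working it through.** **The plan's own power figure.** SAP section 4 gives 375 patients, 66% in GOLD A&B, triple therapy in 24% versus 46%, and two-sided 5%. The groups are 247.5 and 127.5 patients and the pooled rate is 0.66 × 0.24 + 0.34 × 0.46 = 0.3148. The null SE is √[0.3148 × 0.6852 × (1/247.5 + 1/127.5)] = 0.0506 and the alternative SE is √[0.24 × 0.76/247.5 + 0.46 × 0.54/127.5] = 0.0518. Power = Φ[(0.22 − 1.96 × 0.0506)/0.0518] = 99.0%, in line with the stated figure above 98%. It concerns GOLD group, a patient-level factor.

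**Inputs for tier.** About 1500 patients, half stable and half exacerbating (SAP Table 1), are modelled separately, so there are about 750 per model. With 35 sites, m = 750/35 = 21.4 patients per site. The ICC is assumed.

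**Formulas.** Design effect DE = 1 + (m − 1) × ICC. True error of the nominal 5% test = 2 × [1 − Φ(1.96/√DE)]. Effective N = 750/DE. The correct CI on the log-odds scale is √DE times wider, or √DE × 2.035/1.96 with t on 35 − 2 = 33 df.

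| Assumed ICC | DE | True error | Effective N | Widening, normal | Widening, t33 |
|---|---|---|---|---|---|
| 0.01 | 1.20 | 7.4% | 623 | 1.10 | 1.14 |
| 0.02 | 1.41 | 9.9% | 532 | 1.19 | 1.23 |
| 0.05 | 2.02 | 16.8% | 371 | 1.42 | 1.48 |
| 0.10 | 3.04 | 26.1% | 246 | 1.74 | 1.81 |

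With 40 sites the errors are 7.1, 9.2, 15.4 and 23.9%; with 30 sites they are 7.8, 10.7, 18.6 and 28.8%.

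**Example.** Assume 30% prescribed in both tiers, 375 patients per tier and an odds ratio of 1.00. SE(log OR) = √[2/(375 × 0.3 × 0.7)] = 0.159, so the planned CI is 0.73 to 1.37. With t on 33 df it should be about 0.70–1.43, 0.68–1.47, 0.63–1.59 and 0.57–1.76 at the four ICCs.

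**Smaller and larger cases, same ICC order.**
- SAP 6.7.4 compares a treatment with none. If that leaves half the patients (m = 10.7): 6.1, 7.3, 10.8 and 16.3%.
- At 3 months, if a share p of prescriptions still comes from the enrolling hospital and the rest from unrelated ones, DE = 1 + (m − 1) × ICC × p². With p = 0.5: 5.6, 6.2, 8.0 and 11.1%. With p = 0.3: 5.2, 5.4, 6.1 and 7.2%. For stable patients, change is measured from the enrolling hospital's baseline prescription, which this formula ignores, so neither set is firm.
- If site sizes vary with a CV of 0.5, DE = 1 + [(1 + 0.25) × m − 1] × ICC: 8.1, 11.1, 19.5 and 30.0%.

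**Simulation check.** With 35 sites, 750 patients, a 30% base rate, no true tier effect and 4000 runs, an ordinary logistic model with tier and two covariates rejects in 7.0, 10.2, 16.8 and 25.6% of runs. Site-clustered variance with 33 df rejects in 5.2, 5.6, 5.3 and 4.8%. A multinomial outcome split 60/25/15 gives about 8 to 26% ordinary and 4.6 to 6.0% clustered. With 22 parameters the clustered test gives 4.9 to 5.6%, and a bias-corrected version 3.9 to 4.1%. Rare patterns were not simulated.

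**The case against.** **Tier is not a hypothesis of the study.** This stands. The secondary objective names disease severity and socio-economic factors, and the covariate list in Protocol 5.2 does not include tier; the SAP added it. The SAP nevertheless commits to a CI and P-value for it.

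**Read literally, SAP 6.1.4 runs everything by tier, so the problem disappears.** This does not stand. A forced tier term and a Tier 2 versus Tier 3 comparison can only come from pooled data. It is true, though, that the sentence "The above analyses will also be performed for Tier 2 and 3 hospitals separately" covers the change-of-prescription analyses. For the baseline models, pooled runs follow only from the forced term.

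**The ICC is assumed, and availability may vary little.** This stands as a limit on size. Protocol section 1 gives Tier 3 hospitals the full range of COPD therapies, and Protocol 3.2.2 admits only Tier 2 hospitals that supply LAMA and ICS/LABA. Prescribing habits may still differ between sites, but the documents do not measure that.

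**Patients change hospital.** Protocol section 1 puts re-attendance at roughly below 50%. This reduces the effect at 3 months but not for the baseline prescription, which the enrolling hospital writes.

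**Stronger readings.** A reader might infer that only 35 observations remain. The effective N is 623 to 246 at the assumed ICCs, so that goes too far. A reader might also infer that the power claim or the descriptive percentages fail. The power concerns a patient-level factor and reproduces, and the point percentages do not depend on the variance method.

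**Conclusion.** The concern holds for the tier odds ratios, CIs and P-values from the pooled-tier models, and for the tier comparison in SAP 6.7.2(4). The direction is certain for any positive within-tier site correlation; at an ICC of zero the planned intervals are correct. The size is not known from the documents: a true error of about 7 to 26% rests on assumed ICCs of 0.01 to 0.10, about 35 equal sites and about 750 patients per model. At 3 months it is smaller.

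This should be fixed, but it does not threaten the primary objective. By-tier runs are not challenged. Whether the stable-versus-exacerbating comparison in SAP 6.6.1 is affected depends on the cohort mix at each site, which is unknown, and no claim is made about it.

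**What to change.** 1. Reconcile SAP 6.1.4 with 6.7.4 and 6.7.2(4): state that the tier term and the tier comparison come only from runs that pool both tiers.
2. In both model tables of SAP 6.7.4, base the tier CI and P-value on variance clustered on enrolling site, with a small-sample correction and degrees of freedom from the number of sites (about 33). GEE with independence working correlation suits the binary models; cluster-robust variance suits the multinomial one. A random site intercept is acceptable, but its odds ratios are site-specific.
3. State that the univariate P < 0.1 screen keeps its planned model-based P-values. Otherwise clustered variance could change which covariates enter, and with them the adjusted odds ratios. With this rule the selection and the population-averaged odds ratios stay as planned.
4. In SAP 6.7.2(4), replace the chi-square or Fisher test for tier by a site-clustered Rao-Scott or GEE test. Where data are sparse, give n and % by tier without a P-value.

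Reporting ICCs is optional. The cost is SAP text and minor programming; no new data are needed because the enrolling site is known. Tier CIs become about 1.14 to 1.81 times wider at the assumed ICCs, some sparse tables lose a P-value, and a bias-corrected variance is slightly conservative in a large model (about 4% error in simulation).
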